5.6. Subgroups

Subgroup analysis are planned to be performed by sex (female/male) and heart failure ejection fraction (HFrEF/HFpEF).

Heart failure ejection fraction will be defined based on the echocardiogram parameter: LVEF (%). If LVEF values are ≤ 40 then it is 'HFrEF', otherwise if LVEF values is ≥ 50 then it is 'HFpEF'. A separate look will be at the LVEF values is $> 40 - < 50$ as a HFpEF subgroup.

Subgroup analysis is planned for efficacy and safety endpoints, subject disposition, demographics and other baseline characteristics, prior and concomitant medication.

This document is confidential.

6. Demographic, Other Baseline Characteristics and Medication

6.1. Subject Disposition and Withdrawals

Subject disposition will be summarized by presenting the number and percentage of subjects eligible for the study, number of subjects in each analysis set, subjects completed the Month 6, V5 visit, subjects completed the Month 12, V6 visit, and completed or discontinued from the study together with the primary reason for premature termination, compliance with taking Cordella System daily reading per protocol. Additionally, presentation will be done by site.

Major protocol deviations will be summarized. In addition, a table will be generated summarizing the number of percentage of patients with a protocol deviation due to COVID-19.

Furthermore, the number of subjects excluded from each analysis set will be summarized by reason for exclusion.

Subject status at the study visits described in [Appendix 1: Time and Event Schedule](#) will be summarized presenting number of subjects alive, number of subjects with alive status (inpatient hospitalization/out subject), and number of subject with out status (home/rehabilitation centre/other) by visit.

In addition, subject training on Cordella system at implant visit will be presented in a separate table.

All data will be listed.

6.2. Demographic

Demographic (age, gender, race, ethnicity, height, weight, and BMI), heart failure ejection fraction, and smoking history, will be presented in a summary table for mITT, ITT and PP population.

All data will be listed.

6.3. Medical History and Concomitant Diseases

Medical history data will be summarized by category of medical condition for mITT, ITT and PP population. Medical history conditions with ongoing ticked 'No' will be considered as prior diseases, with ongoing ticked 'Yes' as concomitant diseases. In addition, all data will be listed.

Cardiac medical and surgical history data will be summarized by category of cardiac medical and surgical history for mITT, ITT and PP population. In addition, cardiac medical and surgical history will be listed.

6.4. Other Baseline Characteristics

Summary table will be presented for 'Time since first diagnosis of heart failure', 'Type of first heart failure', 'Previous cardiovascular history', and 'Number of hospitalizations in past year for the cardiovascular reasons'

Cardiovascular history data will be summarized by category. In addition, cardiovascular history be listed.

6.5. Medication

All medications will be coded using the WHO Drug Global B3, March 2019.

The number and percentage of subjects taking baseline and concomitant medications will be summarized overall by Anatomical Therapeutic Chemical (ATC) Levels 2 and 3 for mITT, ITT and PP population. All medication will be listed.

6.5.1. Baseline Medication

Medications started prior to the date of implant will be summarized as 'Baseline' medications.

This document is confidential.

6.5.2. Concomitant Medication

Medications taken at/after the date of implant will be summarized as 'Concomitant' medications.

This document is confidential.

7. Efficacy

The population used for efficacy analyses will be the mITT. In addition, all efficacy analysis will be analyzed based on PP population and Cohort #1 population. For CEC related endpoints, tables and figures will be repeated using CEC adjudication results

7.1. Primary Efficacy Endpoint and Analysis

The primary efficacy endpoint is the 6 month incidence of HF related hospitalizations (HFH) or all-cause mortality.

The information on mortality will be used as collected on the CRF, AE page with AE outcome = 'Death' or Study completion page with primary reason for discontinuation = 'Death'.

The information on HF hospitalizations will be used as collected on the CRF, Hospitalization page, only hospitalizations due to heart failure and stay at least 24 h will be considered as HF related hospitalizations

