6.1 Study Flow

The study will implant up to 535 subjects. Assuming a dropout rate of approximately 10% by 6 months, this study will implant a maximum of 450 patients in Cohort #2 and Cohort #3. This is to achieve at least 406 implanted patients with complete follow-up at 6 months. After completion of enrollment and as soon all 406 subjects reach their 6 month follow- up visit, the 6 month primary endpoint data will be used for Premarket Approval (PMA) submission. Up to 85 subjects (cross- over from former **Control Arm**) will continued to be followed in Cohort #1.

[figure not shown]

Figure 9: Study Flow

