where r_6 is the 6 month rate of primary endpoint events and PG_6 is the performance goal. A value of 0.43 will be used for the goal. The null hypothesis will be rejected if the upper confidence bound for the rate is less than the performance goal, or equivalently, that the corresponding p-value from the hypothesis test is less than 0.025. An observed rate of less than 0.37 and rejection of the null hypothesis indicate that the observed rate is statistically less than the performance goal, indicating clinically acceptable results and study success. Analysis will be based on a Poisson regression approach for the number of events, with the log follow-up time as an offset term. Sensitivity analyses using a negative binomial approach to capture within-subject correlation will be performed.

The study will implant 450 subjects (combined in Cohort #2 and Cohort #3) leading to an expected evaluable cohort of 406 subjects. With a goal of 0.43 and a one-sided 0.025 alpha level, the study will have greater than 80% power assuming a population treatment rate of 0.34. Calculations are based on a one-sample Poisson rate test and were performed with PASS 2021.

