13.2.3 CEC

The CEC will adjudicate all events including device malfunctions dynamically. Each event will be adjudicated by an independent CEC committee (at least 3 reviewers) with the final adjudicated result being a consensus of the committee.

The CEC process is documented in the study specific CEC Charter.

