9. PRESSURE SENSOR FAILURE
10. PULMONARY EMBOLISM
11. PULMONARY OCCLUSION
12. RENAL DYSFUNCTION classified as Acute renal dysfunction or Chronic renal dysfunction
13. STROKE (Non-Fatal) AND TRANS ISCHEMIC ATTACK (TIA) classified as Stroke or TIA
STROKE CLASSIFICATION as Ischemic, Hemorrhagic or undetermined
STROKE DEFINITION as Disabling stroke or Non-disabling stroke
14. VASCULAR ACCESS SITE AND ACCESS-RELATED COMPLICATIONS classified as Major vascular complications or Minor vascular complications
15. VESSEL TRAUMA classified as Blunt injury or Penetrating injury
16. OTHER <specify>

All SAEs and some selected AEs will be sent for adjudication.

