	14.2.1.1.8a	SAS-Output: 6-month incidence of HF hospitalizations (HFH) or all-cause mortalities from CEC adjudication results, stratified by heart failure ejection fraction	mITT Population
	14.2.1.1.9	6-month incidence of HF hospitalizations (HFH) or all-cause mortalities from CEC adjudication results	Per Protocol Population
	14.2.1.1.9a	SAS-Output: 6-month incidence of HF hospitalizations (HFH) or all-cause mortalities from CEC adjudication results	Per Protocol Population
	14.2.1.1.10	6-month incidence of HF hospitalizations (HFH) or all-cause mortalities from CEC adjudication results	Cohort #1 Population
	14.2.1.1.10a	SAS-Output: 6-month incidence of HF hospitalizations (HFH) or all-cause mortalities from CEC adjudication results	Cohort #1 Population
	14.2.1.1.11	6-month incidence of HF hospitalizations (HFH) from CEC adjudication results	mITT Population
	14.2.1.1.11a	SAS-Output: 6-month incidence of HF hospitalizations (HFH) from CEC adjudication results	mITT Population
	14.2.1.1.12	6-month incidence of all-cause mortalities from CEC adjudication results	mITT Population
	14.2.1.1.12a	SAS-Output: 6-month all-cause mortalities from CEC adjudication results	mITT Population
	14.2.1.2.2	Sensitivity Analysis - 6-month incidence of HF hospitalizations (HFH) or all-cause mortalities from CEC adjudication results using negative binomial regression model	mITT Population

This document is confidential.

Header	Table Number	Name	Analysis Set
	14.2.1.2.2a	SAS-Output: Sensitivity Analysis - 6-month incidence of HF hospitalizations (HFH) or all-cause mortalities from CEC adjudication results using negative binomial regression model	mITT Population
14.2.2		Secondary Efficacy Parameters	
14.2.2.1		Incidence of HF Hospitalizations or all-cause mortality at 12 months	
	14.2.2.1.1	12-month incidence of HF hospitalizations (HFH) or all-cause mortalities	mITT Population
	14.2.2.1.1a	SAS-Output: 12-month incidence of HF hospitalizations (HFH) or all-cause mortalities	mITT Population
	14.2.2.1.2	12-month incidence of HF hospitalizations (HFH) or all-cause mortalities, stratified by sex	mITT Population
	14.2.2.1.2a	SAS-Output: 12-month incidence of HF hospitalizations (HFH) or all-cause mortalities, stratified by sex	mITT Population
	14.2.2.1.3	12-month incidence of HF hospitalizations (HFH) or all-cause mortalities, stratified by heart failure ejection fraction	mITT Population

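### The SAP implies that site-reported CRF events, not the independently adjudicated ones, decide the primary efficacy test in this open-label single-arm trial, and no sentence fixes the precedence

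*SAP*

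**What the plan says.** **Event source.** SAP 7.1 states: "The information on HF hospitalizations will be used as collected on the CRF, Hospitalization page". It counts only stays of at least 24 h that are due to heart failure. Deaths come from the AE page or the study completion page. SAP 7.1.1, headed as the main analysis, sets out the Poisson test against 0.43 and the further condition that the observed rate be below 0.37. Neither condition names an event source. SAP 8.1.1 likewise reads both primary safety endpoints from the AE CRF page.

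**Adjudication.** Protocol 13.2 makes the CEC independent of the sponsor and the CRO. Protocol 13.2.3 says: "The CEC will adjudicate all events including device malfunctions dynamically". SAP 8.3.3 is narrower: "All SAEs and some selected AEs will be sent for adjudication". Hospitalisation and death are seriousness criteria in protocol 9.1.2, so heart failure admissions and deaths reach the CEC under either text.

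**Use of the adjudicated results.** The opening of SAP section 7 says: "For CEC related endpoints, tables and figures will be repeated using CEC adjudication results". Section 8 says the same for safety. SAP 7.1.3 places separate CEC analyses of heart failure hospitalisation and mortality under supplementary analysis. The table index holds the primary result twice: 14.2.1.1.1 (CRF) and 14.2.1.1.6 (CEC). The CEC versions of the primary safety tables are 14.3.1.1.13 and 14.3.1.2.13.

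**Definition.** For a heart failure hospitalisation, protocol 14.6 requires a primary diagnosis of heart failure and a stay of at least 24 h. It also requires new or worsening symptoms, objective evidence, and started or intensified treatment.

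**The concern.** The sites know that every patient has a sensor, see the pressures and manage to a pressure target. Whether an admission is due to heart failure is partly a judgement. In a randomised comparison, a shared tendency to over- or under-attribute would partly cancel between arms. Here there is no control arm, so any net misattribution passes directly into the comparison with 0.43.

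The plan already produces the same test on independently adjudicated events but does not let that version decide. It also has no rule for the case where one version meets the success criteria and the other does not. What is at stake is which event count determines study success.

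**Working it through.** **1. Inputs.** Protocol 10.3 takes 0.34 as the assumed event rate: "With a goal of 0.43 and a one-sided 0.025 alpha level, the study will have greater than 80% power assuming a population treatment rate of" that value. The study implants 450, "leading to an expected evaluable cohort of 406 subjects". Protocol 6.1: "Assuming a dropout rate of approximately 10% by 6 months". Check: 406/450 = 0.902, consistent with about 10% loss. The second success condition is an observed rate below 0.37.

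**2. The plan's own power figure.** For an exact one-sample Poisson test, take the largest c with P(X ≤ c | mean 406 × 0.43 = 174.58) ≤ 0.025. This gives c = 148, with an attained level of 0.0220. Power is P(X ≤ 148 | mean 406 × 0.34 = 138.04) = 81.4%. The stated figure of more than 80% reproduces.

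**3. Largest event count that still succeeds.** The upper 95% limit on the log scale is (c/N) × exp(1.96/√c).

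| N | c | Rate | Upper limit | Below 0.43? | Rate below 0.37? |
|---|---|---|---|---|---|
| 406 | 148 | 0.3645 | 0.428 | yes | yes |
| 406 | 149 | 0.3670 | 0.431 | no | yes |
| 450 | 166 | 0.3689 | 0.4295 | yes | yes |
| 450 | 167 | 0.3711 | 0.432 | no | no |

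The exact upper limit gives the same cut-offs, 148 and 166.

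**4. Distance from expectation to failure.**
- N = 406: expected 406 × 0.34 = 138; the first failing count is 149; the difference is 11, and 11/138 = 8.0%.
- N = 450: expected 450 × 0.34 = 153; the first failing count is 167; the difference is 14, and 14/153 = 9.2%.

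This is a distance to the boundary. It is not an estimate of how far CRF and CEC counts will differ.

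**5. Illustration under assumed net differences.** The documents give no discordance rate, so the percentages below are assumptions. N = 406 and the cut-off is 148.

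| True rate | Net change in the deciding count | P(success) |
|---|---|---|
| 0.34 | −10% | 98.3% |
| 0.34 | −5% | 93.3% |
| 0.34 | none | 81.4% |
| 0.34 | +5% | 62.1% |
| 0.34 | +10% | 39.8% |
| 0.43 | none | 2.2% |
| 0.43 | −5% | 8.7% |
| 0.43 | −10% | 24.8% |

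Each entry is P(X ≤ 148) for a Poisson mean of 406 × rate × (1 + change).

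**6. Why the counts can differ.** SAP 7.1 needs a heart failure reason and 24 h. Protocol 14.6 adds symptoms, objective evidence and treatment. If the CEC applies 14.6, which is an assumption because its charter is not among the documents, it can remove admissions that the CRF rule keeps. It can also add heart failure admissions that a site attributed to another cause. All-cause death needs no attribution, so adjudication should hardly change it.

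**The case against.** **The CRF version is already the main one.** A reader might infer two competing primary results and freedom to choose between them afterwards. The documents do not support that. SAP 7.1 names one source, 7.1.1 is the main analysis, the CEC tables are described as repeats, and the separate CEC analyses are supplementary. The natural reading is that CRF events decide. What stands is that this is only implied, and that it is the weaker choice of source for this design.

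**The negative binomial table.** The only 6-month entry in the index reads "Sensitivity Analysis - 6-month incidence of HF hospitalizations (HFH) or all-cause mortalities from CEC adjudication results using negative binomial regression model". One might infer a planned mismatch with a CRF-based main analysis. It looks more like a dropped row: numbering starts at 14.2.1.2.2 with no 14.2.1.2.1, the 12-month endpoint has both versions, and SAP 7.1.2 calls for the same terms as the main model without limiting it to CEC data.

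**Adjudication coverage.** A reader might infer that non-serious sensor failures or IV-diuretic visits escape the CEC because the SAP sends it only selected non-serious AEs. That gap is not shown. CEC tables are planned for sensor failure (14.3.1.2.13 onward) and for IV-diuretic visits (14.2.2.6.26-30 and 14.2.2.9.6-10), and listing 16.2.7.4 covers adjudicated predefined events. The SAP wording is looser than protocol 13.2.3, no more.

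**Direction.** The looser CRF definition would, taken alone, raise the CRF count and make success harder. Under-attribution by unblinded sites would do the opposite. Bias in the sponsor's favour is therefore not shown.

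**Limits of adjudication.** A committee can reclassify events it receives. It cannot recover events that sites never report, so it reduces misclassification and does not remove it.

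**Conclusion.** The point holds as a cheap improvement. The plan implies that unadjudicated, site-attributed hospitalisations decide a single-arm comparison with a fixed goal, while an independent version of the same result is already planned as a repeat and no precedence is stated. The margin is narrow: 11 events at 406 full exposures, or 14 at 450, separate the planned expectation from failure.

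This rests on a true rate of 0.34, Poisson variation and full exposure for 406 or 450 subjects. The size and direction of any CRF-CEC difference are unknown, and the exposure lies almost entirely in heart failure attribution. Sample size, alpha and the stated power do not change with the event source, so this is not a sizing error.

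**What to change.** 1. In SAP 7.1 and 7.1.1, name CEC-adjudicated heart failure hospitalisations and deaths (table 14.2.1.1.6) as the single deciding source for both the Poisson test and the 0.37 condition. Label table 14.2.1.1.1 a sensitivity analysis.
2. In SAP 8.1.1, do the same for the two primary safety endpoints: tables 14.3.1.1.13 and 14.3.1.2.13 decide, and the CRF versions become sensitivity analyses.
3. State that the named source governs if the two versions disagree, and that both will be reported.
4. Run the 6-month negative binomial sensitivity analysis on the same source as the main analysis, and correct the index accordingly.
5. As wording clean-up only, align the adjudication scope in SAP 8.3.3 with protocol 13.2.3.

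The cost is SAP wording and table relabelling, since the CEC tables are already indexed. Adjudication must be complete before the primary lock.

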7.1.1. Main analysis

The mathematical statement of the null and alternative hypothesis is as follows:

$$H_0: r_6 \geq PG_6$$

$$H_A: r_6 < PG_6$$

will be used for the goal. The null hypothesis will be rejected if the upper confidence bound for the rate is less than the performance goal, or equivalently, that the corresponding p-value from the hypothesis test is less than 0.025. An observed rate of less than 0.37 and rejection of the null hypothesis indicate that the observed rate is statistically less than the performance goal, indicating clinically acceptable results and study success. Analysis will be based on a Poisson regression approach for the number of events, with the exposure time as an offset term, where r_6 is the 6-month rate of primary endpoint events and PG_6 is the performance goal. A value of 0.43 will be used for the goal.

The test will be based on each subject's total number of events, treatment arm, and exposure time, where a subject's exposure is the time to death, early study discontinuation or 6 months, whichever is smaller.

```
proc genmod data = xxx;  
    model number of events = dummy /*(dummy variable)*/ / noint type3 dist=poisson  
offset=log(exposure_time);  
run;
```

All events until day x, which would be exact 6 months (180 days) post-implant visit would be summarized by cohort. The estimated 6 month incidence of HF related hospitalizations (HFH) or all-cause mortality, along with the 2-sided 95% CIs for the estimated will be presented, and p-value from the hypothesis test. The presentation will also include number of HFH, all-cause mortality, total number of both events, and subjects' event rate of HFH or all-cause mortality is calculated as the total number of observed events per subject divided by the (subject's observed exposure time/180) from implant through 6 months, where a subject's exposure is the time to death, early study discontinuation or 6 months (180 days) post implant visit, whichever is the smallest.

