This document is confidential.

study success. Analysis will be based on a Poisson regression approach for the number of events, with the log follow-up time as an offset term. Sensitivity analyses using a negative binomial approach to capture within-subject correlation will be performed.

The study will implant 450 subjects (combined in Cohort#2 and Cohort#3) leading to an expected evaluable cohort of 406 subjects. With a goal of 0.43 and a one-sided 0.025 alpha level, the study will have greater than 80% power assuming a population treatment rate of 0.34. Calculations are based on a one-sample Poisson rate test and were performed with PASS 2021.

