5.5. Pooling of Sites

Subjects will be pooled across sites for analysis of study endpoints. Sites with at least 20 subjects will retain their identities. Smaller sites will be ranked in decreasing order of size (site identification numbers, smallest first, will be used to break ties) and cumulatively pooled until pooled sites of no less than 10 subjects are achieved. After this pooling process, it will be tested for homogeneity in the treatment effects across site by using the same poisson model for primary endpoint but to add pooled site as a covariate. The homogeneity test will be conducted at the 0.15 level effect for pooled_site.

```
proc genmod data = xxx;  
    class pooled_site;  
    model number of events = pooled_site / type3 dist=poisson  
        offset=log(exposure_time);  
run;
```

In case homogeneity in the rate across sites is not given, an explorative analysis will be performed as post-hoc analysis, to evaluate in a first step what are the differences between the sites which may lead to different rates across sites. The possible factors will be evaluated during this exploratory analysis. In a second step a more complex analysis, e.g. Bayesian hierarchical model of HF event rates across pooled sites which is

This document is confidential.

essentially treating site as a random effect could be performed. The final decision on the analysis to be performed will be evaluated outside of this SAP. Pooling of sites will be based on the mITT and PP populations.

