7.1.2. Sensitivity analysis

Sensitivity analyses using a negative binomial approach (with the same terms as the poisson model used in the main analysis) to capture within-subject correlation will be performed.

This document is confidential.

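### The 6-month success bound takes its width from a plain Poisson variance for repeat heart failure events plus death; if events cluster within subjects, the one-sided error exceeds 2.5%

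*SAP*

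**What the plan says.** SAP 7.1.1 sets the main analysis: "Analysis will be based on a Poisson regression approach for the number of events, with the exposure time as an offset term". The count is each subject's total, so repeat hospitalisations and death all contribute. Exposure ends at death, discontinuation or 180 days. The GENMOD call specifies a Poisson distribution with a log-exposure offset, without a scale option or a REPEATED statement. On the goal the SAP says "A value of 0.43 will be used for the goal". Success requires an upper confidence bound below that value (p < 0.025) and an observed rate below 0.37.

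The sample size uses the same variance. Protocol 10.3 states: "Calculations are based on a one-sample Poisson rate test and were performed with PASS 2021". SAP 2.4.1 gives the design as "one-sided 0.025 alpha level, the study will have greater than 80% power assuming a population treatment rate of 0.34", with 450 implants "leading to an expected evaluable cohort of 406 subjects".

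SAP 7.1.2 then plans "Sensitivity analyses using a negative binomial approach", with the stated purpose of capturing within-subject correlation. No rule says what follows if that model and the Poisson model disagree. The SAP's Index of Tables lists this check at 6 months only for adjudicated events (Table 14.2.1.2.2: "Sensitivity Analysis - 6-month incidence of HF hospitalizations (HFH) or all-cause mortalities from CEC adjudication results using negative binomial regression model"), whereas SAP 7.1 builds the main analysis on CRF events. At 12 months the index lists both versions. SAP 7.1.4 applies the same Poisson approach to the 12-month endpoint.

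**The concern.** A Poisson model fixes the variance of the event count at its mean. If some patients are readmitted repeatedly and many not at all, the true variance is larger, the model-based standard error is too small and the upper bound is too low. The error then runs in one direction: a device whose true rate equals the performance goal passes too often.

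The trial is a single arm with one primary efficacy test. By Protocol 6.1 its 6-month result supports the PMA submission, and by SAP 2.4.2 it also opens formal testing at 12 months. The plan names the dependence that would invalidate the bound, yet lets the model that ignores it decide.

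**Working it through.** **Inputs.** Goal 0.43, assumed true rate 0.34, one-sided 0.025, 406 evaluable of 450 implanted (SAP 2.4.1 and 7.1.1); about 10% dropout by 6 months (Protocol 6.1). Dispersion is not in the documents. Assumption: negative binomial counts with variance = mean × (1 + k × mean), k from 0 to 3.

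**The plan's own figure.** One-sample Poisson test, normal approximation:

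power = Φ{[(0.43 − 0.34)√406 − 1.96√0.43] / √0.34} = 81.8%.

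The exact Poisson calculation gives 81.4%. The stated power of more than 80% is reproduced when variance equals mean.

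**Cut-off of the written rule.** For D events in n subject-periods, the rate is r = D/n and the Poisson upper bound is r × exp(1.96/√D).

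- D = 148: 0.3645 × exp(1.96/√148) = 0.428, below 0.43.
- D = 149: 0.3670 × exp(1.96/√149) = 0.431, not below.

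So success needs at most 148 events in 406 subjects. The rate there, 0.3645, already satisfies the 0.37 condition. With 450 full exposures the cut-off is 166, or 0.3689, again below 0.37. The Poisson bound alone decides.

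**Error under clustering.** The total over n subjects is negative binomial with size n/k and mean n × rate. Example for k = 1 at the goal: mean 406 × 0.43 = 174.6, variance 174.6 × 1.43 = 249.6, P(D ≤ 148) = 4.6%. With Poisson variance the same probability is 2.2%.

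| k | variance/mean at 0.43 | error, written rule, 406 | power, written rule, 406 | power, written rule, 450 with dropout | power, robust bound, 406 |
|---|---|---|---|---|---|
| 0 | 1.00 | 2.2% | 81.4% | about 84% | about 81% |
| 0.25 | 1.11 | 2.8% | 80.5% | about 83% | about 78% |
| 0.5 | 1.22 | 3.4% | 79.6% | about 82% | about 75% |
| 1 | 1.43 | 4.6% | 78.2% | about 80% | about 69% |
| 2 | 1.86 | 7.0% | 75.8% | about 78% | about 58% |
| 3 | 2.29 | 9.2% | 74.1% | about 77% | about 51% |

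The first two result columns are exact. The last two are simulated. The dropout column assumes 450 implanted with about 10% leaving uniformly over 6 months, giving about 428 subject-periods. The robust bound is r × exp(1.96 × SE), with SE = √Σ(yᵢ − r tᵢ)² / D over subjects; in 20,000 simulated trials per setting its error was 2.2% to 2.7% up to k = 2 and about 3% at k = 3.

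**Effect on one result.** At an observed rate of 0.36 in 406 subjects (D = 146), the bound is 0.36 × exp(1.96√(φ/146)), where φ is variance/mean: 0.423 at φ = 1, 0.439 at 1.5 and 0.453 at 2. The same data pass or fail depending on the variance used.

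**12 months.** These sizes do not carry over. At 0.59 × 406 = 239.5 events the Poisson bound is 0.59 × exp(1.96/√239.5) = 0.670, already below 0.70. The 0.59 condition is therefore stricter than the bound there and gives some protection. The bound and p-value still rest on the same variance.

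**The case against.** The strongest reply is that the size is unknown. No passage supports any particular k; at k = 0 the rule is valid, and at k = 0.1 the error is still 2.4%. The 7% to 9% figures need a variance about 1.9 to 2.3 times the mean. This stands: a reader might infer that the trial's error is 7% to 9%, and the documents do not support that.

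Second, clustering is not ignored. The negative binomial model is prespecified in Protocol 10.3 and in SAP 2.4.1, 7.1.2 and 7.1.4. This also stands. The missing 6-month table for CRF events is a gap in the index and does not cancel SAP 7.1.2. What remains is that the model has no role in the decision.

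Third, a reader might infer that power collapses. The stated power belongs to the written test, and that moves little: 81% to 78% at k = 1 on 406 subjects. The mITT set is all implanted subjects and dropouts contribute exposure, so about 80% is kept up to k = 1 on that basis. The large losses belong to a test that holds the error.

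Fourth, it is tempting to extend the point to every analysis from SAP 7.1.6 to 7.1.12. Sections 7.1.7, 7.1.10 and 7.1.11 are descriptive or Kaplan-Meier and contain no Poisson model. The site homogeneity test in SAP 5.5 does use one, but a positive result leads only to exploratory work, and its false-positive rate depends on pool sizes that the documents do not give.

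**Conclusion.** The concern holds conditionally. The deciding bound in SAP 7.1.1 is anti-conservative if events cluster within subjects, and the plan itself anticipates such correlation. On 406 subjects the error passes 2.5% between k = 0.1 (2.4%) and k = 0.25 (2.8%), and reaches 4.6% at k = 1. The 0.37 condition adds no protection at 6 months. These figures assume gamma-distributed differences in subject event rates and full 180-day follow-up; simulation with dropout gives similar errors (4.6% at k = 1).

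The power statement is correct only with variance equal to mean. Its weakness is secondary: the written rule roughly keeps its power under moderate clustering, but does so at an error above the stated level.

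**What to change.** - **SAP 7.1.1 and 7.1.4:** keep the pooled rate (events over exposure) as the estimate. Take the deciding upper bound and p-value from one named method, the by-subject robust (sandwich) variance, using one record per subject and GENMOD REPEATED SUBJECT. A negative binomial bound should not be left as an alternative: with unequal exposure it weights subjects differently and need not return the pooled rate.
- **SAP 7.1.2:** keep plain Poisson and negative binomial as sensitivity analyses. Add the 6-month negative binomial table for CRF events to the index.
- **SAP 7.1.6, 7.1.8, 7.1.9 and 7.1.12:** use the same robust variance; these analyses are nominal.
- **Protocol 10.3 and SAP 2.4.1:** restate 6-month power as about 81% without overdispersion, with the lower figures over a stated dispersion range.

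The cost is SAP wording, one line of code, a wider interval and a less favourable stated power. If the counts prove to be Poisson, almost nothing is lost: power stays at about 81%. No extra patients are proposed. The price of that choice should be stated: keeping 80% power with a valid bound would need 389.4 × φ subjects, that is 467 at φ = 1.2, 584 at 1.5 and 779 at 2.0.
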